## **8.9 Qualitative assessments – Nested studies**

### **8.9.1 Implementation process evaluation**

Prior to the implementation of our intervention we will research the barriers and facilitators to the use of an online CPOE and the use of order sets to guide the implementation approach. This will be assessed involving a purposive sample of various stakeholders: physicians, clinical biologists and information technologists. The GUIDES checklist (Van [name] 2016) will be used to guide the interview and the data analysis. This checklist identifies 18 factors spread over 4 domains that influence the effectiveness of CCDSS. We will assess our intervention and the implementation of our intervention for each of these factors. The information obtained from these qualitative assessments will be used to tailor the CPOE and the order sets to maximise acceptance, usability and

effectiveness. We will report on our implementation strategy using the GUIDES checklist as backbone in a process evaluation.

### 8.9.2 Sustainability of implementation impact

Six months after the end of the intervention period, all participants will receive our intervention. This cross-over is motivated by two reasons: first, the laboratories perceive this intervention as a service to their customers. They cannot consent to withholding a substantial portion of their clients to this service. Moreover, prolonging the study period may demotivate participants in the control group. Second, we would like to measure the sustainability of our intervention over time in the intervention arm. **The cross-over will allow us to lengthen the follow-up period for the physicians in the initial intervention arm.**

### 8.9.3 Downstream activities

We will include one exploratory outcome in our study, this being the effect of evidence-based order sets on downstream or cascade activities. Literature suggests that improving appropriateness of laboratory testing has an effect which is much larger than simply on the amount of tests ordered. It reduces the amount of unnecessary testing due to deviant tests of unknown significance. This effect on over-diagnosis and downstream or cascade activities is often referred to as the 'Ulysses effect' (Rang 1972). Some exploratory studies have shown that the Ulysses effect may not be as important in primary care as literature suggests, but good evidence remains lacking. Evaluating these downstream or cascade effects is a resource-intensive work as this can only be done through manual review of data extracted from the EHR and completed with direct patient interviews. In a subset of 250 laboratory panels, we will review the corresponding patient charts and identify all those activities originating directly from the results of the ordered laboratory tests. We will use the methods by Houben et al (Houben 2010) as a guide to identify those laboratory panels that could potentially lead to downstream or cascade activities. We will focus on inappropriate tests in both the control and intervention arm to evaluate the extent of downstream activities and compare the difference in downstream or cascade activities between abnormal and normal results. This outcome will be measured 6 months after the initial laboratory test order. This data will also be used in any cost-effectiveness analysis resulting from this trial.

### 8.9.4 Physician satisfaction

There are signals that increasing eHealth initiatives are increasingly complicating daily medical practice and that this has a negative influence on physicians' professional satisfaction (Shanafelt 2016). Belgium too has known a strong increase in the use of EHRs, CPOEs and other electronic aids in health care. However, little is known on the impact of this increased electronic environment on physicians, in particular general practitioners.

In the final stages of our trial we will survey the physicians participating in the study to evaluate their satisfaction. We will design the survey during the follow-up period of the trial and send it to the participants after the final data extraction has taken place. The aim of the survey is to evaluate 2 questions:

1. How do physicians perceive the transition from a paper-based laboratory order form to an online CPOE?
2. Does the addition of evidence-based order sets facilitate the use of an online CPOE?

## 8.10 Withdrawal criteria

We do not foresee any withdrawal criteria for our study physicians. Study physicians are free to use or not to use the intervention. Adherence to the intervention will be a measure of implementation success. We will monitor the use of paper-based orders alongside the CPOE as an additional measure of implementation success.

## 8.11 Storage and analysis of samples

All data from the collaborating laboratories and all data extracted from patients through the online data extraction form or through chart review will be stored on a secured server hosted by the UZ Leuven/KU Leuven. Access to this database will be restricted to the members of the research facility to ensure the protection of patient data. This database will not include any names or detailed patient data. All data will be collected and stored using the reference number allocated to the patient and their blood sample by the collaborating laboratory.

Consent from the sectoral committee of the Federal Privacy Commission will be sought prior to the start of the study.

## 8.12 End of trial

Where necessary, end of trial documents and notifications will be drafted and presented.

# 9 STATISTICS AND DATA ANALYSIS

## 9.1 Sample size calculation

Our study involves multiple levels which are not independent of each other. Lowest on the level of analysis is the individual laboratory test included in our study. We must account for the fact that these tests are not ordered entirely independent of each other in one patient, for instance, a white blood cell count is often ordered together with a white blood cell differentiation. In our analysis we will account for this level of clustering. Additionally, there is clustering on the level of the physician. When the same physician orders tests for various patients over time, each of these orders is not independent of the other. For instance, if a physician often requests chloride in patients taking diuretics, then this will probably be so in all patients taking diuretics. We must therefore also account for clustering on the level of the physician. Finally, GP's often work in primary care practices. Physicians working in the same practice tend to have similar ordering behaviour implying that the orders made by two physicians in the same practice are not independent of each other. This is the last level of clustering for which we will account. We therefore have a 4 level setting comprising test, patient, physician and primary care practice:

1. Multiple study tests per patient, assumed to be 5 per patient,
2. Multiple patients per physicians, assumed to be 42 per 3 months if there is 70% use of the online intervention,
3. Multiple physicians per primary care practice (PCP), assumed to be 2.35 based on preliminary data by Heselmans et al ([Heselmans 2013](#)).

Each of these clustering levels inflates the required sample size.

These levels are important because we will analyse at the level of the patient or the test (depending on the outcome), but we will recruit physicians and allocate primary care practices. We have calculated our sample size and translated this to the amount of physicians to be recruited and the duration of the study. For these calculations we have made several assumptions based on data from various sources ([De Sutter 2007](#), [Janssens 2014](#)). First, we assume that the average test panel will include 5 study tests. Second, we assume that during the study period each test panel will correspond to one patient (that there will be no multiple test panels per patient). Third, we assume that each physician orders blood tests for 15 patients per week. Fourth, we assume that physicians will use the intervention in 70% of the situations (implying a 30% usage of paper-based orders) based on figures by van Wijk et al ([van Wijk 2001](#)). Fifth, we assume that a primary care practice includes 2.35 physicians, based on the recruitment data from an ongoing cluster randomized trial in primary care ([Heselmans 2013](#)).

### 9.1.1 Primary outcome appropriateness

*To compare the effect of evidence-based order sets for 17 study indications versus control on the proportion of appropriate laboratory tests ordered by primary care physicians.*

Null hypothesis: evidence-based order sets for 17 study indications have no effect on the proportion of appropriate laboratory tests ordered by primary care physicians compared to control.

Alternative hypothesis: evidence-based order sets for 17 study indications will increase the proportion of appropriate laboratory tests ordered by primary care physicians from 70% to 80% compared to control.

Figures and statistics on appropriateness of laboratory testing are grossly lacking, due to heterogeneity in the definition of appropriateness and differences in appropriateness criteria depending on the type of test. A robust figure, that seems reiterated in various studies, is that the proportion inappropriate laboratory tests is found to be around 30% (Zhi 2013, van Walraven 1998). It is believed that when using order sets in a CPOE, the appropriateness of laboratory ordering will improve. We propose that the trial should have 80% power to detect a 10% difference (in this case, from 30% to 20%) using a significance level of 5%. Appropriateness will be measured as the proportion of inappropriate study tests recorded through the CPOE. The unit of randomization is the PCP and not the patient or test, hence it is necessary to account for the lack of independence between the various tests, patients treated by the same physician and physicians working in the same PCP. In our design we account for clustering on multiple levels; clustering on the level of the individual tests ordered for the same patient, clustering for ordering patterns of the same physician for different patients and clustering for ordering patterns of physicians practicing within the same PCP. Estimates of intraclass correlation coefficients (ICCs) for process of care measures in primary care are between 0.05 and 0.15 (Campbell 1999, Campbell 2000), however estimates for ICCs regarding appropriateness of laboratory tests have been shown to vary between 0.04 and 0.288 (Littenberg 2006). To our knowledge no ICCs have been published for clustering on the various levels observed in our trial, therefore we have chosen to use a very conservative ICC estimate of 0.2 for each level of clustering in our sample size calculations, probably overestimating the design effect. Using methods proposed by Campbell (Campbell 2004) we would need 586 tests over both arms if unadjusted for clustering. We hypothesize that each panel will include approximately 5 study tests and that physicians will order laboratory tests for 42 patients per 3 months using the CPOE, assuming a 70% usage of the CPOE (van Wijk 2001). To account for clustering on the PCP level, we assume 2.35 physicians per PCP based on preliminary data from an ongoing trial (Heselmans 2013). In this situation the amount of tests would be inflated to 7305 tests, or 35 physicians in a trial lasting 3 months, taking into account multi-level clustering and attenuation of the clustering due to the amount of measures per patient (Teerenstra 2008). Figure 15 summarises the sample size calculations for the outcome appropriateness and their assumptions.

Sample size for comparison of 2 proportions (binary values): 2-sided equality

Appropriateness: pA: 70%

Clinically significant change of 10% (to pB: 80%)

$\alpha = 0.05$

$1-\beta = 0.80$

$K = 1$

Sample size: 586

Sample size calculations based on Campbell et al (Campbell 2004) for a trial with 80% power to detect a difference of 10% (increase of appropriateness from 70% to 80%) with a significance of 10% predict 586 tests.

Design effect of clustering on sample size based on Teerenstra et al (Teerenstra 2008):

4 level setting comprising test, patient, physician and primary care practice:

1. Multiple study tests per patient, assumed to be 5 per patient,
2. Multiple patients per physicians, assumed to be 42 per 3 months if there is 70% use of the online intervention and 1/3 indications included in the study,
3. Multiple physicians per primary care practice (PCP), assumed to be 2.35 based on preliminary data by Heselmans et al. (Heselmans 2013)

We assume an intracluster coefficient of 0.2 for each level of clustering.

$Rho_n$  = correlation between two physicians active in the same PCP

$Rho_s$  = correlation between two patients cared for by the same physician

$Rho_e$  = correlation between two tests ordered for the same patient

$n_n$  = mean amount of physicians per PCP

$n_s$  = mean amount of patients per physician

$n_e$  = mean amount of study tests per patient

$Phi_e = 1 + Rho_e * (n_e - 1)$

$Phi_s = 1 + Rho_s * (n_s - 1) * w_e$

$Phi_n = 1 + Rho_n * (n_n - 1) * w_n$

$w_e = (n_e * Rho_e) / (1 + Rho_e * (n_e - 1))$

$w_s = (n_s * Rho_s) / (1 + Rho_s * (n_s - 1))$

The final design effect (DE) =  $Phi_e * Phi_s * Phi_n$

Applied to our protocol:

$n_n$  = mean amount of physicians per PCP = 2.35

$n_s$  = mean amount of patients per physician = 42 per 3 months

$n_e$  = mean amount of study tests per patient = 5

$Phi_e = 1 + Rho_e * (n_e - 1) = 1.8$

$Phi_s = 1 + Rho_s * (n_s - 1) * w_e = 5.56$

$Phi_n = 1 + Rho_n * (n_n - 1) * w_n = 1.25$

$w_e = (n_e * Rho_e) / (1 + Rho_e * (n_e - 1)) = 0.56$

$w_s = (n_s * Rho_s) / (1 + Rho_s * (n_s - 1)) = 0.913$

The final design effect (DE) =  $Phi_e * Phi_s * Phi_n = 1.8 * 5.56 * 1.25 = 12.465$

586 test \* 12.465 (DE) = 7305 test = 1460 patients = 35 physicians during 3 months

Figure 15: Sample size calculations for primary outcome appropriateness including inflation due to multi-level clustering

### 9.1.2 Secondary outcome 'missed or delayed diagnoses'

To demonstrate non-inferiority in the effect of evidence-based order sets for 17 study indications versus control on the incidence of missed or delayed diagnoses by primary care physicians.

Null hypothesis: evidence-based order sets for 17 study indications increase the incidence of missed or delayed diagnosis in primary care by more than 1%.

Alternative hypothesis: evidence-based order sets for 17 study indications do not worsen the incidence of missed or delayed diagnoses by primary care physicians compared to control, i.e.  $p_A - p_B < 1\%$ , with  $p_A$  and  $p_B$  being the proportion of missed diagnoses in the intervention and control groups, respectively.

To our knowledge there are no sound statistics on the percentage missed diagnoses due to laboratory testing in primary care. Panesar et al (Panesar 2016) estimated that two to three per hundred consultations in primary care result in safety incidents. Between 4 and 45% of these safety incidents may be related to misdiagnosis or missed diagnoses. Assuming 2.5% missed diagnoses in primary care, we calculated that the trial, with an 80% power to detect a non-inferiority of a 1% difference using a significance level of 5%, would need 6032 patients in total. Previous studies have illustrated that in primary care ICCs for clinical outcomes are lower than those for process outcomes and the ICC for adverse effects to be around 0.025 (Adams 2004). Although this may not seem correct, the chances that a physician consistently misses the same diagnosis is less probable than consistently ordering the same test for the same indication. A missed or delayed diagnosis will more probably lead to a change in practice than over- or underutilization of a laboratory test. For this outcome, the unit of analysis will be individual patients and not individual tests as for appropriateness. Therefore, there is one level of clustering less to account for. Assuming a 3 month period in which laboratory tests are ordered for 42 patients, we would need to recruit 290 physicians. In the case of a 6 month period, implying 84 patients for which a laboratory panel is requested, we would need to recruit 220 physicians. For this clinical outcome we will not account for clustering on the level of the PCP as there is no evidence that this influences the amount missed diagnoses by individual physicians. Intuitively, there is no reason to assume that two physicians working together in the same practice would have a greater probability of missing the same diagnosis. Because we believe this outcome to be important in convincing physicians in the widespread use of order sets for laboratory tests, we have chosen to power our study to include this outcome. Figure 16 summarises all the sample size calculations for the outcome 'missed or delayed diagnoses' and their assumptions.

Sample size for comparison of 2 proportions (binary values): non-inferiority trial  
 Missed diagnoses: pA: 2.5%  
 Missed diagnoses: pA: 2.5%  
 Clinically significant change of 1%  
 $\alpha = 0.05$   
 $1-\beta = 0.80$   
 $K = 1$   
 Sample size: 6032  
 Sealed Envelope Ltd. 2012. Power calculator for binary outcome non-inferiority trial. [Online] Available from: <https://www.sealedenvelope.com/power/binary-noninferior/> [Accessed Wed Jul 20 2016].  
 $DE = 1 + \rho(n-1)$   
 $n$  = number individuals per cluster  
 $\rho$  = intracluster correlation coefficient  
 We account only for the clustering on the level of the physician.  
 $n = 42$  for a trial lasting 3 months  
 $n = 84$  for a trial lasting 6 months  
 $\rho = 0.025$   
 for a trial lasting 3 months:  $DE = 2.025$  which implies **290 physicians ( $\approx 300$  physicians)**  
 for a trial lasting 6 months:  $DE = 3.075$  which implies **220 physicians**

**Figure 16:** Sample size calculations for secondary outcomes missed or delayed diagnoses including inflation due to clustering

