#### 3.3.2 Secondary endpoints/outcomes

##### 3.3.2.1 Diagnostic error

Due to the role of the GP as a gateway keeper, caring for a variety of complex patients, he is vulnerable to diagnostic errors (Kostopoulou 2008). Diagnostic errors are defined as diagnoses that were unintentionally delayed, wrong or missed (Graber 2005). In a classification of diagnostic error, amongst the most important reasons for diagnostic error in laboratory testing were the failure or delay in ordering needed tests and ordering of the wrong tests (Schiff 2009). Previous studies (Hickner 2014) have shown that fear of malpractice or liability influences the test ordering behaviour of physicians. Despite the vulnerability of primary care for diagnostic error, incidences remain low. Very little reliable figures on diagnostic error due to laboratory testing exist, but several studies estimate it less than 0.1% (Singh 2013) to 2.5% (Panesar 2015). An important concern in the interpretation of these results lies in the fact that they are often based on retrospective analyses with hindsight bias (Zwaan 2013). Despite these apparently low figures, fear of diagnostic error (and related liability) is an important concern for physicians when ordering laboratory tests (Hickner 2014). Our secondary aim is to demonstrate that improving appropriateness of laboratory testing does not result in more diagnostic errors.

To date, there is no standardised way of measuring diagnostic error. The Core Outcome Measures in Effectiveness Trials (COMET) initiative has no registered outcomes concerning diagnostic error and no guidelines on how to detect diagnostic error exist ([www.comet-initiative.org](http://www.comet-initiative.org)). The review by Kostopoulou et al (Kostopoulou 2008) analysed studies on diagnostic delay of solitary conditions. All of the included studies were retrospective studies looking backward at the medical history of patients with the same diagnosis and analysing the (delay in the) diagnostic process preceding the diagnosis. Singh et al (Singh 2013) used a novel approach to defining diagnostic error through creating an

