2.2.2. Secondary objective: diagnostic error

To demonstrate non-inferiority in the effect of evidence-based order sets versus control on the incidence of missed or delayed diagnoses for 17 common indications by primary care physicians.

Null hypothesis: evidence-based order sets increase the incidence of missed or delayed diagnoses in primary care by more than 1%.

Alternative hypothesis: evidence-based order sets do not worsen the incidence of missed or delayed diagnoses by primary care physicians compared to control, i.e. $p_A - p_B < 1\%$, with p_A and p_B being the proportion of missed diagnoses in the intervention and control groups, respectively.

Population: patients for which laboratory tests were ordered for 17 common indications by primary care physicians

Intervention: CPOE with evidence-based order sets

Comparison: CPOE without evidence-based order sets

Outcome: incidence of missed or delayed diagnoses related to the 17 indications

Time: continuously during 6 months following initial laboratory test ordering

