10.1.2. Secondary outcome diagnostic error

This outcome is defined in 2 independent ways.

The first is based on the physician's evaluation. During data collection, for every new diagnosis, physicians were asked whether it was related to the laboratory panel and, if so, whether the diagnosis was made correctly and timely. If the physician gives a negative answer to this question, this diagnosis is marked as 'possible diagnostic error'.

The second definition is based on a theoretical evaluation, by two independent researchers, of all occurring combinations of new diagnoses and indications for lab panels. For each combination an algorithm (see figure 2) will be applied in order to become an evaluation of 'no' or 'possible' diagnostic error. In case of dispute, a third independent researcher will be asked to resolve the evaluation. The researchers involved in this theoretical evaluation will be blinded to the allocation of the intervention until all evaluations have been made and validated.

[figure not shown]

Figure 3: Algorithm used for the theoretical evaluation of diagnostic error.

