10.2.2. Secondary outcome analysis

Diagnostic error

The proportion of patients with a missed diagnosis will be analysed by means of a logistic GEE model that includes allocated group and laboratory as factors and uses PCP as the clustering variable. An independent working correlation matrix will be used. The proportion of patients with a missed diagnosis and associated 95% confidence intervals will be estimated from the model.

The difference in proportions will be obtained by subtracting the two proportions. The associated standard error will be calculated from the rules for the variance of a difference between two independent estimates. The 95% confidence interval for the difference will be calculated.

The non-inferiority limit for missed diagnoses is 1%, i.e. the intervention will be deemed non-inferior if the difference between the allocated groups (intervention – control) is less than 1%. Therefore, the intervention will be deemed non-inferior if the upper limit of the 95% confidence interval lies below 1.

As for the primary endpoint, the analysis will be performed for all 17 study indications together. An additional analysis will be performed that only includes patients who have no indications in addition to the 17 study indications

Test volume

The total number of tests will be analysed using a GEE model for count data (Poisson or Negative Binomial to handle potential overdispersion) that includes allocated group and laboratory as factors in the model and PCP as clustering variable. No offset will be used. The number of tests per patient for each group will be estimated from the model and presented together with their associated 95%

confidence intervals. The effect of the intervention will be presented as the ratio between the two numbers with its 95% confidence interval. Statistical significance will be assessed at a significance level of 5%.

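### Does the loosely sourced 2.5% missed-diagnosis rate make the fixed 1-point non-inferiority margin unsound?

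*Protocol*

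**What the plan says.** Protocol 9.1.2 opens by admitting that sound statistics on missed diagnoses due to laboratory testing in primary care are lacking. It then cites a review in which "two to three per hundred consultations in primary care result in safety incidents" and continues: "Between 4 and 45% of these safety incidents may be related to misdiagnosis or missed diagnoses. Assuming 2.5% missed diagnoses in primary care". With a 1-point margin, 80% power and 5% significance this gives 6,032 patients before clustering. The inflation uses an ICC of 0.025 at physician level only: "For this clinical outcome we will not account for clustering on the level of the PCP".

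Protocol 3.3.2.1 introduces the rate differently: "Very little reliable figures on diagnostic error due to laboratory testing exist, but several studies estimate it less than 0.1" per cent, with 2.5% as the upper end of the range. The same section later plans telephone interviews for about 315 patients with a diagnostic error, at an assumed rate of 2.5%.

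SAP 2.2.2 says that order sets "do not worsen the incidence of missed or delayed diagnoses by primary care physicians compared to control, i.e. $p_A - p_B < 1" per cent, observed "continuously during 6 months following initial laboratory test ordering". Under SAP 10.1.2, a new diagnosis that the physician relates to the panel but judges not to have been made correctly and on time counts as follows: "this diagnosis is marked as 'possible diagnostic error". SAP 10.2.2 estimates the proportion in each arm and their difference, all with 95% confidence intervals, and sets the rule: "the intervention will be deemed non-inferior if the upper limit of the 95% confidence interval lies below 1" (percentage point).

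**The concern.** Three things look wrong together.

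- **The rate has two descriptions.** It is the top of a range for laboratory-related diagnostic error in one place. In the other it equals the middle of the range for all safety incidents, with the 4 to 45% diagnostic share left out.
- **Neither source is in the endpoint's unit.** The endpoint is patients with an event over six months. One source is per consultation and the other gives no denominator, so the true control rate could lie below or above 2.5%.
- **The margin is absolute.** If the control rate is low, 1 point is a large relative rise. The rule looks only at the upper limit, so an interval lying wholly between 0 and 1 point would satisfy a hypothesis worded as not worsening, although the data show an increase.

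Protocol 9.1.2 says the trial is powered for this outcome because it matters in persuading physicians to use order sets. A reassuring label on a demonstrated increase would undercut that purpose.

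**Working it through.** **1. Reproduce the planned size.** With 2.5% in both arms, margin 0.01, one-sided alpha 0.05 and 80% power:

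n per arm = (1.645 + 0.842)² × 2 × 0.025 × 0.975 / 0.01² = 3,014, so 6,028 in total against 6,032 stated. With DE = 1 + 0.025 × 41 = 2.025, 6,032 × 2.025 / 42 = 290.8 physicians, against 290 stated. The figures follow from the inputs. The formula matches only at one-sided 5%; at one-sided 2.5%, which corresponds to the 95% interval rule, it gives 7,654. That is a separate matter and does not bear on this point.

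**2. Compare the rates.** Applying the diagnostic share in Protocol 9.1.2 gives 2% × 4% = 0.08% up to 3% × 45% = 1.35% per consultation. This is not a better planning rate: several consultations per patient over six months would raise it, and the documents give no number of consultations. Counting possible errors could raise it too. The plan's per-patient assumption can be recovered from Protocol 3.3.2.1: 2.5% × 12,600 = 315.

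**3. Size of the margin in relative terms**, (p + 1)/p with p in per cent:

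| Control rate | Fold-rise equal to 1 point |
|---|---|
| 5% (illustrative) | 1.2 |
| 2.5% | 1.4 |
| 1.35% | 1.74 |
| 1% | 2.0 |
| 0.5% | 3.0 |

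**4. When can the rule pass an increase?** A result passes if d + 1.96 × √[p(1−p)/n + (p+d)(1−p−d)/n] < 0.01. Here n = N/(2 × DE) is the effective number per arm, DE = 1 + 0.025 × (m − 1) and m is the mean cluster size. For an interval to lie wholly between 0 and 1 point, its half-width must be below 0.5 points. The highest control rate that allows this is found at d = 0.5 points. An observed doubling is d = p.

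| Patients / clusters | m | DE | n per arm | Doubling passes at or below | Interval above 0 passes below |
|---|---|---|---|---|---|
| 12,600 / 300 physicians | 42 | 2.025 | 3,111 | 0.55% | 0.77% |
| 11,200 / 280 physicians | 40 | 1.975 | 2,835 | 0.54% | 0.68% |
| 9,520 / 280 physicians | 34 | 1.825 | 2,608 | 0.52% | 0.61% |
| 12,600 / 124 practices | 101.6 | 3.515 | 1,792 | 0.46% | 0.34% |
| 11,200 / 72 practices | 155.6 | 4.864 | 1,151 | 0.38% | 0.13% |
| 9,520 / 72 practices | 132.2 | 4.281 | 1,112 | 0.38% | 0.11% |

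The 12,600 patients and 124 practices are the protocol's plan. The 11,200 patients, 280 physicians and 72 practices come from SAP 3.2 and 3.3. The 9,520 is 11,200 less the 15% without an eForm (SAP 10.3). The practice rows borrow 0.025 as an assumption, because the documents give no practice-level ICC for this outcome.

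**5. Examples.**

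- 0.5% against 1.0% with n = 3,111: √[(0.004975 + 0.0099)/3,111] = 0.00219, times 1.96 = 0.00429. The interval is 0.07 to 0.93 points, so it passes and excludes zero. In the practice rows the same rates fail, with upper limits of 1.06 to 1.22.
- 2.5% in both arms with n = 3,111: √(0.04875/3,111) = 0.00396, times 1.96 = 0.78 points. The whole interval is 1.55 points wide and cannot fit between 0 and 1. At a control rate of 2.5% the largest observed rise that passes is 0.21 to 0.14 points in the physician rows. In the practice rows the intervention must look better than control.

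**6. Does a low rate harm the test?** No. At 0.5% in both arms the step 1 formula needs 1,232 patients before clustering, against 6,028 at 2.5%.

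**The case for a change.** The strongest case for a change is that the two descriptions of 2.5% cannot both be right and the cited range reaches below 0.1%, so low control rates cannot be dismissed. At such rates the plan would attach a reassuring label to an interval that excludes zero. Reporting wording settled after database lock, when SAP section 8 unblinds the study team, would look chosen to suit the result. A relative risk and two sentences on reporting would cost almost nothing.

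The textual inconsistency stands, and so does the conditional arithmetic. The rest loses its force for four reasons.

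- The reassuring phrase never stands alone. Protocol 3.2.1 and 9.1.2 and SAP 2.2.2 each define it as a difference below 1 point, against a null of an increase of more than 1%. The decision rule itself speaks only of non-inferiority.
- An interval between zero and the margin is possible in any non-inferiority trial with enough precision. It is not a fault of this one.
- SAP 10.2.2 already puts both proportions and the difference, with intervals, in the report. An increase would be in plain view, and the ratio of the two proportions is one division away.
- The protocol already discloses the uncertainty in the rate. SAP 3.4 times collection of the diagnostic-error data to end in June 2019, so rewriting the sample-size rationale would alter no patient count, margin or rule.

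**Conclusion.** No change is needed. The two accounts of 2.5% are a drafting inconsistency in the rationale, and the unstated relative size of the margin is a detail any analyst can supply from the planned output. Followed as written, the plan supports a sound conclusion: a positive result means that an absolute increase of 1 point or more has been excluded, at whatever control rate is observed.

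The awkward case, an interval above zero that still passes, needs a control rate below about 0.6 to 0.8% with the protocol's physician-level ICC, or about 0.1 to 0.3% if the same ICC applied between practices. It cannot occur at the planned 2.5%. These limits assume equal arms, equal cluster sizes and a normal approximation, and the practice-level figures are a range rather than an estimate. The control rate per patient over six months cannot be derived from the documents. If it proves low, the authors should discuss the relative size of the margin when they interpret the result, and the planned estimates let them do so.
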